1.2.1.2.2 Overview of safety

In the clinical trials for the treatment of hypertension or primary hyperaldosteronism, osilodrostat was tolerated with the overall incidence of adverse events being similar to placebo.

Adverse events (AEs) were generally of mild to moderate intensity. Both Serious Adverse Events (SAEs) and discontinuations due to AE were infrequent, and were reported at a rate

similar to placebo in the hypertension studies. The most common AEs across these studies were: headache, dizziness (including postural dizziness), nausea, diarrhea and fatigue. There were also AEs of hyperkalemia and impaired ACTH-stimulated cortisol response in these trials, which are consistent with the potential for hypocortisolism and hypoaldosteronism.

Overall, in patients with CD (study CLCI699C2201), safety data from the 10-week analysis has also showed that osilodrostat was well tolerated with similar common AEs to those in the hypertension trials, including: fatigue, nausea, vomiting, diarrhea, headache, dizziness, hypokalemia and muscle spasms.

In Part I of the study, all 12 patients (100%) experienced adverse events but these were generally grade 1 or grade 2 (National Cancer Institute Common Terminology Criteria (NCI CTC)). Fatigue, muscle cramps, dizziness and gastrointestinal events were the most common events suspected to be drug related. Four patients reported AEs consistent with cortisol and/or aldosterone withdrawal; dose reductions or temporary dose interruption in these patients improved the symptoms. There were no discontinuations related to study drug and no serious adverse events of suspected drug relationship.

In Part I, SAEs of decreased hemoglobin, tachycardia, chest pain and reactivation of Takayasu's arteritis were reported in one patient. The events were attributed to progression of the preexisting conditions and were not suspected to be related to study drug.

In Part II, osilodrostat was also generally well tolerated throughout the study. Of the 19 enrolled patients, 17 patients completed the 22 weeks treatment period with a median duration of exposure of 25.1 and 38.9 weeks in the Expansion cohort and Follow-up cohort, respectively. The safety findings identified in the interim analysis (data cut-off date: 23-Dec-2013) that was performed after the last patient had completed 22 weeks of treatment showed that except for one patient in the Expansion cohort, all patients experienced AEs, grade 1 and grade 2 in most of the cases. Adrenal insufficiency, nausea, fatigue and increase levels of oxycorticosteroids, blood corticotrophin, and blood testosterone were the most common AEs suspected to be drug related [by Preferred Term]. There were no new safety concerns during the Extension Period to Month 31. This study is ongoing.

In Part II (31-month analysis), a total of 9 SAEs were reported in 4 patients, including (by preferred term) pituitary-dependent Cushing's syndrome (in 2 patients), electrocardiogram QT prolonged, food poisoning, gastroenteritis, headache, non-cardiac chest pain, pituitary tumor and pituitary tumor benign.

Of these, one event of QT prolongation was reported as related to study drug by the Investigator, however the event developed in the context of gastroenteritis with anorexia and dehydration. There were no reported cardiac symptoms or cardiac arrhythmia. QT prolongation resolved after osilodrostat was discontinued, and did not reoccur when osilodrostat was re-started at a lower dose.

Other notable events included pituitary tumor enlargement and pituitary tumor reported in two patients. Both patients had elevated ACTH level. The study treatment was stopped in both patients because of pituitary surgery. The Investigators did not suspect a relationship between the events and treatment with osilodrostat.

In reviewing the clinical trial experience with osilodrostat to date, AEs have been identified that are consistent with the mechanism of action of the drug as an inhibitor of both cortisol and aldosterone synthesis. These can be summarized as follows:

- Changes in adrenal hormones: cortisol decreased, aldosterone decreased, and their precursors (11-deoxycortisol, 11-deoxycorticosterone) increased
- Change in pituitary hormone: ACTH increased
- Changes in electrolytes: potassium increased or decreased
- Changes in body weight and blood pressure: potentially increased by mineralocorticoid effect of the aldosterone precursor 11-deoxycorticosterone
- Changes in sex hormones: testosterone and estradiol increased (testosterone more than estradiol)

In addition, treatment with osilodrostat can potentially result in neutropenia, which is considered to be an indirect effect of cortisol reduction, as reported in the literature. During hormonal control, a significant decrease of neutrophil count, which is commonly elevated in patients with CD, has been reported demonstrating the effect of glucocorticoids on these blood cells ([Masri-Iraqi et al 2014](#)). This effect has also been observed with osilodrostat in the CD trials and has included cases of neutropenia which were associated with cortisol levels that were either below normal or have had a rapid and substantial decline from baseline. In the cases observed to date, neutropenia has rapidly reversed with discontinuation of osilodrostat, and has also reversed when osilodrostat was continued, typically with decreasing doses.

For a comprehensive review of clinical safety data with osilodrostat, see the [\[Investigator's Brochure\]](#).

1.2.1.2.3 Osilodrostat: QT/QTc in healthy volunteers

The potential impact of osilodrostat on cardiac repolarization potential was assessed in the definitive ICH E14 compliant thorough QT Study (TQT) study LCI699C2105 in 86 healthy male and female subjects.

Based on the predicted exposure levels, the predicted maximum mean QTcF on osilodrostat 30 mg is 6.3 ms (CI 5.13, 7.42).

The results remained below the QTcF effect of regulatory concern (i.e., an upper boundary of the 90% CI < 10 ms) and fully support the use of LCI699 doses up to 30 mg b.i.d.

2 Objectives and endpoints

Objectives and related endpoints are described in [Table 2-1](#) below.

Table 2-1 Objectives and related endpoints

Objective(s)	Endpoint(s)
Primary Objective(s) 
• To evaluate long term safety data	Endpoint(s) for primary objective(s) 
• Frequency and severity of AEs/SAEs;
Secondary Objective(s) 
• To evaluate clinical benefit as assessed	Endpoint(s) for secondary objective(s) 
• Proportion of patients with clinical benefit as assessed by the Investigator at scheduled visits

Objective(s)	Endpoint(s)
by the investigator. • To evaluate long term safety data	• Frequency, severity and summaries of relevant safety assessments. Safety assessments include: laboratory evaluations, vital signs (blood pressure and body weight), ECG and pituitary MRI.

3 Study design

3.1 Description of study design

This is a multi-center, open label phase IIb study to evaluate the long-term safety of osilodrostat in subjects receiving osilodrostat in a Global Novartis-sponsored study which has fulfilled its requirements for the primary objective, and who are judged by their parent study Investigator as benefiting from continued treatment with osilodrostat.

There will be no screening period for this study. Eligible subjects can start their treatment with osilodrostat as soon as they are enrolled in the study. The first study visit will be scheduled at the time of the last study visit for the parent study. At that time, sufficient supply of osilodrostat to cover a period of approximately 3 months may be dispensed to the subject/caregiver or as per local practice.

[figure not shown]
Subjects must return to the study center at least on a quarterly basis (every 12 weeks \pm 2 weeks) for safety and clinical benefit assessments, and resupply of study medication. Drug dispensing and administration information and adverse events will be collected. The subject may return to the clinic at any given time as per standard of care or treating physician recommendation; however, only the quarterly study visits will be recorded in the Case Report Form (CRF). Study medication dispensed will be recorded in the CRF dose administration page.

All adverse events and serious adverse events, including pregnancy, will be collected throughout the study.

The study is expected to remain open for approximately 5 years (or until 31-December-2023 in the UK) from First Patient First Visit (FPFV). Subjects will continue to be treated in this roll-over study until they are no longer benefiting from their osilodrostat treatment as judged by the Investigator or until osilodrostat is commercially available or until one of other discontinuation criteria is met (please refer to [Section 9.1.1](#)). At every quarterly visit (every 12 weeks \pm 2 weeks), the Investigator is required to confirm that the subject continues to have clinical benefit and may continue receiving study treatment.

A subject will reach the end of study when osilodrostat treatment is permanently discontinued.

Figure 3-1 Study Design

4 Rationale

The purpose of this study is to evaluate the long-term safety of osilodrostat and to allow its continued supply to subjects who are currently receiving osilodrostat treatment in a Global Novartis- sponsored study that has reached its study objectives.

These subjects are judged by the parent study Investigator as benefiting from continued treatment with osilodrostat and by the fact that, they would not be able to access osilodrostat outside a clinical trial.

4.1 Rationale for study design

This is a multi-center, open-label, phase IIb roll-over study to evaluate the long-term safety of osilodrostat in subjects who have completed the parent studies and are judged by the parent study Investigator as benefiting from treatment.

This roll-over study will not include a screening phase, at the completion of the parent study, as subjects will directly transfer from the parent studies. When their participation in the parent study has finished, eligible patients will start receiving osilodrostat only after they have signed the Informed Consent and have met the selection criteria for this roll-over study.

4.2 Rationale for dose/regimen and duration of treatment

At the time of transition to this roll-over study, the starting dose should be the same as the last dose that was given at the last visit in the parent study. During the roll-over study, dose modification may be done at the discretion of the Investigator following the guidelines in [Section 6.5](#).

The maximum dose may not exceed 30 mg bid, which is the same maximum dose also applied in the parent studies.

Osilodrostat (LCI699) will be given in form of film-coated tablets for oral administration, and available in the following dose strengths: 1 mg, 5 mg and 10 mg.

4.3 Rationale for choice of control drugs (comparator/placebo) or combination drugs

Not applicable.

4.4 Purpose and timing of interim analyses/design adaptations

Not applicable.

4.5 Risks and benefits

There is still an unmet need in the treatment of CD: despite available therapies, a substantial number of subjects do not achieve normalization of cortisol, lose biochemical control over time or present medication-related adverse reactions and may stop treatment because of this.

In order to mitigate the potential risks related to the administration of osilodrostat, some procedures will be taking place:

- The starting dose should be the same as the dose provided in the parent osilodrostat study at the time of transition to the roll-over study. However, the investigator can change the dose based on the subject's response; the maximal dose should not exceed 30 mg b.i.d.
- Subjects will be evaluated by the treating investigator for clinical benefit and safety based on the following assessments:
 - Physical examination (every 12 weeks)
 - Body weight / blood pressure (every 12 weeks), 12-lead safety ECG (every 24 weeks), blood chemistry and hematology (every 24 weeks), 11-deoxycortisol and 11 deoxycorticosterone (every 24 weeks), testosterone (every 24 weeks), Urinary Free Cortisol (UFC) (every 12 weeks), serum cortisol as clinically indicated, plasma ACTH (every 12 weeks) and pituitary MRI (every 48 weeks or more frequently if clinically needed).
- AEs and SAEs will be reported continuously and evaluated by the investigator at each visit.
- Drug administration record for dosing of osilodrostat will be completed at baseline and during treatment visits.
- For females, urinary pregnancy test will be performed at each visit (every 12 weeks) and monthly, at home.
- Upon administration of the last drug dose, discontinuation from the study or study end, the patient will have a follow-up visit 30 days later.
- The protocol provides specific guidance for dose modifications and/or stopping rules, due to osilodrostat-related toxicities. In addition, a safety follow-up for liver toxicity and management of QT prolongation have also been included.

Potential subject benefits

There is an unmet medical need in subjects with CS since this is a rare and serious disease but with limited medical treatment options.

An open label, proof-of-concept, single-arm study (CLCI699C2201, LINC 2) has been conducted to assess the safety and tolerability of osilodrostat in patients with CD after 10 weeks of treatment.

In this study, 12 CD patients received osilodrostat orally for 10 weeks. The drug was given at the starting dose of 2 mg b.i.d., and was progressively increased on the basis of the urinary

cortisol levels till their normalization or a maximum dose of 50 mg b.i.d. was achieved. After 10 weeks of treatment, all 12 patients normalized urinary cortisol levels or achieved a > 50% reduction in urinary cortisol levels. The reduction of urinary cortisol levels was accompanied by a trend towards a decrease in BP. Osilodrostat was generally well tolerated, with the most frequently reported adverse events being fatigue (58.3%), nausea (41.7%), diarrhea (25%), headache (25%), hypokalemia (25%), muscle spasms (25%) and vomiting (25%).

Recently, an amended extension of the phase II study (CLCI699C2201, LINC 2) is currently ongoing with the overall objective of evaluating the efficacy and safety of osilodrostat for a longer period of time. After 22 weeks of treatment, 15 out of 19 patients (78.9%) had normalized UFC. The decrease in urinary cortisol levels was associated with improvements in the glucose and lipid profiles. Adverse events during this extension of the study included GI disturbances (nausea and diarrhea in 31.6%), asthenia (31.6%) and adrenal insufficiency (31.6%), together with an increase in ACTH, cortisol and aldosterone precursors, and an increase in testosterone, which, in some women was associated with onset or worsening of acne and hirsutism.

There was a trend toward improved fasting glucose and HbA1c in patients with diabetes at baseline, and an improved fasting lipid profile in patients with dyslipidemia at baseline.

After the initial 22 weeks (core study), patients were invited to enter the extension study up to month 31. Safety and efficacy results have shown that the drug's profile will fulfill the unmet need in the medical management of endogenous hypercortisolism because:

- Normal UFC was maintained for >2.5 years in a majority of patients.
- None of the patients with normalization of cortisol experienced escape from response
- Clinical measures improved, particularly body weight and BMI
- Occurrences of the most commonly reported AEs decreased over time

Therefore, osilodrostat seems to be a promising drug for the treatment of CD, with a satisfactory safety and tolerability profile.

Risks of osilodrostat treatment in study population

Known risks of treatment with LCI699 in patients with CS include: QT prolongation, hypocortisolism/adrenal insufficiency, AEs related to the accumulation of precursor molecules, including: increased or decreased blood pressure, hypokalemia or hyperkalemia, hyponatremia, weight gain, edema, and increase in the synthesis of sex steroids (primarily adrenal androgens in women) that may lead to menstrual changes and hirsutism in women and acne in either men or women. Skin rash has been observed. Corticotroph tumor progression, with or without compressive symptoms, is a potential risk.

Neutropenia has been observed in a small number of patients with CD receiving osilodrostat. Preliminary assessment suggests that these events might be associated with cortisol levels that are either below normal or have had a rapid and substantial decline from baseline. In the observed cases, neutropenia rapidly reverses either spontaneously (typically after dose decrease) or with discontinuation of osilodrostat.

In addition, the protocol provides specific guidance for safety follow-up for liver toxicity (increased transaminases, increased total bilirubin) and an algorithm for monitoring and management of QT prolongation.

Conclusion

The treatment of patients with CS still represents a challenge: the available treatments do not lead to biochemical control in quite a large number of patients and many of them lose biochemical control over time.

Therefore there is an unmet medical need to develop new drugs with improved safety, efficacy and a more patient-friendly profile.

Based on current safety and efficacy data of osilodrostat, the overall benefit-risk of trial participation is expected to be positive for all subjects to be enrolled in this study.

5 Population

The investigator or designee must ensure that only patients who meet all the following inclusion and none of the exclusion criteria are offered treatment in the study.

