### 7.1.1 Primary endpoint

The assessment of safety will be based mainly on the frequency and severity of AEs, AESI and SAEs. See also Section 7.5.

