#### *Adverse events of special interest / grouping of AEs*

The specific categories of AEs of special interest list for LCI699 are listed in attachment 8.1.

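### The AESI term list in SAP Attachment 8.1 does not match the known risks in Protocol 4.5, so grouped AESI counts can fall short of the risk described

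*Protocol*

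**What the plan says.** Protocol 4.5 (risks in the study population) names as known risks the AEs tied to precursor accumulation, among them "increased or decreased blood pressure, hypokalemia or hyperkalemia, hyponatremia, weight gain, edema". The same sentence continues with increased sex-steroid synthesis that "may lead to menstrual changes and hirsutism in women and acne in either men or women". Two further effects are described only as observed: "Skin rash has been observed" and, in the next paragraph, "Neutropenia has been observed in a small number of patients with CD receiving osilodrostat".

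Protocol 1.2.1.2.2 summarises the events that fit the drug's mechanism. It names potassium in both directions ("Changes in electrolytes: potassium increased or decreased") and gives a possible rise in body weight and blood pressure as an effect of the aldosterone precursor 11-deoxycorticosterone.

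SAP 7.1.1 states: "The assessment of safety will be based mainly on the frequency and severity of AEs, AESI and SAEs". SAP 7.4 repeats this without severity. The AESI definition in SAP 7.4.1 is one sentence: "The specific categories of AEs of special interest list for LCI699 are listed in attachment 8.1". Attachment 8.1 is a fixed list of preferred terms in five groups. It gives no reason for which terms are in and which are out.

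**The concern.** The precursor group in Attachment 8.1 carries almost the same label as the risk in Protocol 4.5, so a reader of the study report will take its patient count as the frequency of that risk. The AESI tables are also the only outputs that give one patient count per risk across several preferred terms. A patient whose only relevant event is weight gain or a menstrual disorder is not in the precursor count. A patient whose only relevant event is hyperkalaemia, hyponatraemia or hypotension is in no AESI count at all.

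The omitted effects are ones the protocol itself singles out. Table 6-2 lists hypotension, hyperkalemia and weight gain among suspected toxicities, with weight gain and edema in the same row. Section 9.1.1 includes hyperkalemia and hyponatremia among its discontinuation criteria.

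**Working it through.** The plan states no AESI rate, event count or sample size, so there is no figure to reproduce. The check compares two lists.

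**Step 1: size of the list.** Attachment 8.1 has 28 precursor, 14 arrhythmogenic, 11 hypocortisolism, 31 pituitary and 3 QT terms: 28 + 14 + 11 + 31 + 3 = 87.

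**Step 2: search all 87 terms for each effect in the precursor and sex-steroid part of the Protocol 4.5 sentence.**

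| Effect in Protocol 4.5 | Terms in Attachment 8.1 | Other planned output besides the AE tables |
|---|---|---|
| Raised blood pressure | 5 (three pressure-increased terms, two hypertension terms) | Notable values, SAP 7.4.3 |
| Low blood pressure | 0 | Notable values, SAP 7.4.3 |
| Low potassium | 3 | CTCAE grades, SAP 7.4.2 |
| High potassium | 0 | CTCAE grades, SAP 7.4.2 |
| Low sodium | 0 (two terms for high sodium) | CTCAE grades, SAP 7.4.2 |
| Weight gain | 0 | Increase of at least 10%, in the SAP 7.4.4 heading line |
| Oedema | 4 | None |
| Menstrual changes | 0 | None |
| Hirsutism | 1 (plus related hair terms) | None |
| Acne | 1 | None |

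Five named effects have no term in any group. Neutropenia and rash also have none.

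**Step 3: look for a selection rule.** Coverage elsewhere does not explain the choice: raised pressure and low potassium have vital-sign or laboratory tables and are still AESI. Origin within the protocol sentence does not explain it either: hirsutism and acne are in, while menstrual changes from the same clause are out. For sodium, the list holds only the direction that Protocol 4.5 does not name.

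**Step 4: direction and possible size.** Let q be the proportion of patients with at least one listed term in a group, and p the proportion with at least one added term. Adding terms raises the group's incidence by between 0 (every affected patient already has a listed term) and min(p, 1 − q) (no overlap, as far as possible). Under independence the rise is p(1 − q). The documents give neither p nor q, so these values are assumptions:

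- q = 75%, p = 2%: 0.02 × 0.25 = 0.5 points
- q = 50%, p = 10%: 0.10 × 0.50 = 5 points (50% to 55%)
- q = 25%, p = 20%: 0.20 × 0.75 = 15 points

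The count can only rise or stay the same. How far it rises is unknown.

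**Step 5: interim outputs.** SAP 2.3 cuts the interim preferred-term tables at 10% of patients (all AEs) and 5% (suspected related). Take the 100 patients enrolled at 8 April 2020 (Protocol, Amendment 02) and an assumed true incidence of 5% for one term. The chance of fewer than 10 affected patients is the sum over x = 0 to 9 of C(100, x) × 0.05^x × 0.95^(100 − x) = 0.97. Such a term would usually be absent from the all-AE interim table. It would remain in the system-organ-class counts and the patient listings, and in the SAE or related-AE tables where it qualified.

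**The case against.** The strongest objection is about mechanism. Protocol 1.2.1.2.2 ties hyperkalemia to hypocortisolism and hypoaldosteronism, and gives the precursor effect on weight and blood pressure an upward direction. Protocol 1.2.1.2.1 names hypocortisolism, hypoaldosteronism and precursor accumulation as separate changes. Attachment 8.1 follows that logic: raised pressure, low potassium, high sodium, oedema and androgen effects. A reader of Protocol 4.5 alone might infer that all five missing effects belong in the precursor group. The rest of the protocol does not support that, and merging opposite effects would give a count that is hard to interpret. This part stands, and it decides the form of the fix. It does not explain the absence of weight gain, which the protocol attributes to a precursor, or of menstrual changes. Nor does it explain why the opposite-direction effects appear in no AESI group.

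A second objection is that nothing is lost. Every omitted event enters the treatment-emergent AE and SAE tables (SAP 7.4.1). Potassium, sodium, low pressure and weight are also tabulated from measured data, which can catch changes never reported as AEs. This largely stands. Menstrual change has no measured-data route, and none of these outputs gives the grouped patient count.

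A third is that a sponsor may choose a narrower AESI list, and that this one has already been used for the interim safety reports. That is true, and it is a reason to keep the list. The SAP does not, however, say that the narrower scope is deliberate or why.

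**Conclusion.** The mismatch is confirmed term by term. Weight-increase and menstrual terms are missing from the precursor group, and hyperkalaemia, hyponatraemia and low blood pressure are missing from every AESI group. Grouped AESI counts can therefore be lower than the risk described in Protocol 4.5. The shortfall cannot be determined from the documents and may be zero. The 0.5 to 15 points in the working rest on assumed incidences and on independence.

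Three stronger readings are tempting and not supported:

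- **That the primary endpoint is understated.** Protocol Table 2-1 and SAP Table 5-1 define it as frequency and severity of AEs/SAEs, and omitted terms are counted there in full. Only the AESI outputs are affected.
- **That a particular understatement, for instance 5 to 15 points, can be claimed.** Assuming that 5–15% of patients have only omitted terms gives that answer by construction, and it rules out zero without evidence.
- **That neutropenia is an omitted known risk.** Protocol 4.5 describes it as observed in a few patients, outside the known-risk sentence, and calls the assessment of its link to falling cortisol preliminary.

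The study is descriptive and tests no hypothesis. The consequence is for the reading of the AESI tables, not for any formal conclusion.

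**What to change.** Keep the current Attachment 8.1 groups unchanged, so that the final tables can be compared with the interim outputs prepared for the periodic safety reports. Add to the final AESI tables and listings:

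- **(a) An extended precursor row:** the 28 current terms plus the preferred terms for weight increased and menstrual disorders.
- **(b) A separate row, not merged with the precursor group:** hyperkalaemia/blood potassium increased, hyponatraemia/blood sodium decreased, and hypotension/blood pressure decreased.

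Report current and extended counts side by side. A neutropenia row is optional. Fix the added terms in Attachment 8.1 before the final analysis. Record in SAP Section 3 that they come from Protocol 4.5 and were added after interim data had been seen.

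The cost is a longer term list, extra table rows and somewhat higher reported AESI rates, which the side-by-side layout explains. No new data are needed.
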